#### **5.1.6.5. Date of death**

If the date of death is completely or partially missing, the last date of survival is used to impute the date of death:

- If the date of death is completely missing, the last date of survival + 1 is used to impute the date of death
- If the day or both month and day are missing, the date of death = max (the last date of survival + 1, the following date imputed)
  - The day is missing: 01-MM-YYYY
  - The month and day are missing: 01-01-YYYY

## **5.2. Study Subjects**

The population involved in the statistical analysis in the study subjects section is based on all populations who have and have not received systemic first-line treatment, as well as all enrolled subjects.

### **5.2.1. Disposition of subjects**

For all subjects who have signed the informed consent and participated in screening period, descriptive summary will be conducted to summarize the screening status of population subjects, including the number and percentage of screening failures, which will be categorized by the reasons of screening failure.

All enrolled subjects are summarized using frequency and percentage, based on the population who have and have not received systemic first-line treatment, as well as the total population.

In addition, in the disposition of subjects, the frequency and percentage will be summarized for the following information according to the grouped population and the total population:

- Number of enrolled subjects (number of subjects receiving the treatment/number of subjects not receiving the treatment);
- Number of subjects discontinuing the treatment/reasons for treatment discontinuation;
- Number of subjects discontinuing the study/reasons for study discontinuation;
- Number of subjects in each analysis set (full analysis set, safety analysis set, evaluable analysis set, and PD-L1 analysis set).

### **5.2.2. Demographics**

Descriptive statistical summary is conducted by age, gender, ethnicity, body height [cm], weight [kg], body mass index (BMI) [ $\text{kg}/\text{m}^2$ ], and others of subjects. A detailed listing is provided.

The continuous variables such as age, body height, weight, and BMI are summarized by using descriptive statistics such as the number of evaluable subjects (n), mean, standard deviation, median, minimum (min), maximum (max), and quartile (Q1 and Q3).

Gender, ECOG PS, Child-Pugh score classification (5 and 6 points), HBV infection (baseline positive HBsAg), baseline alpha fetoprotein level ( $< 200 \text{ ng/mL}$  and  $\geq 200 \text{ ng/mL}$ ;  $< 400 \text{ ng/mL}$  and  $\geq 400 \text{ ng/mL}$ ), drinking history (yes, no, unknown), and other categorical variables are descriptively summarized by using the number of evaluable subjects and the percentage of corresponding total number of subjects.

Descriptive statistics such as median, quartile (Q1 and Q3), maximum, and minimum of baseline sum of target lesion diameter values (IRC assessment) and baseline sum of target lesion diameter values (investigator assessment) are summarized.

The age will be calculated as the number of full years between the date of birth and the signing date of the informed consent. Age (years) = (date of signing the informed consent - date of birth) / 365.25, and one decimal place will be reserved.

The BMI calculation formula is: BMI (kg/m^2) = baseline weight (kg) / baseline body height (m^2).

### **5.2.3. Tumor diagnosis**

Related descriptive statistics are used to summarize the following tumor indexes: the number and percentage of subjects under each disease name/symptom. In addition, number of subjects and percentage of the degree of differentiation, presence of extrahepatic metastasis, presence of vascular invasion, Barcelona stage, presence of cirrhosis of liver, clinical T/N/M stage, and course of disease (month) in each group will be summarized separately. A detailed list of subjects for tumor diagnosis is provided.

The course of disease (month) is defined as the time from the date of first pathological diagnosis to the date before first administration. The calculation formula is: (The date of first administration - the date of first pathological diagnosis + 1) / 30.4375.

### **5.2.4. Medical history**

Medical history is summarized separately according to populations. In addition, a detailed list of subjects is provided.

### **5.2.5. Tumor treatment history**

Tumor treatment history mainly includes history of tumor surgery, radiotherapy, interventional therapy, local ablation therapy, other local treatments and systemic treatment.

For tumor treatment history, the following descriptive statistics are provided:

- Number and percentage of subjects who have previously received any of the above tumor treatments
- Number and percentage of subjects who have previously received any local treatments (surgery, radiotherapy, interventional therapy, local ablation or other local treatments)
- Number and percentage of subjects who have previously received any local treatments (radiotherapy, interventional therapy, local ablation or other local treatments)
- Number and percentage of subjects who have previously received any local treatments (surgery, interventional therapy, and local ablation)
- Number and percentage of subjects who have previously received tumor surgery

- Number and percentage of subjects who have previously received radiotherapy
- Number and percentage of subjects who have previously received interventional therapy
- Number and percentage of subjects who have previously received local ablation therapy
- Number and percentage of subjects who have previously received systemic therapy
- Number and percentage of subjects who have previously received other local treatments
- Number and percentage of subjects who have previously received systemic therapy with different treatment outcomes (outcomes of first use of sorafenib)

In addition, a detailed list of subjects is provided.

#### **5.2.6. Prior therapy and concomitant medication**

All previous medication, concomitant medication, and concomitant non-drug therapy are listed. ATC1 and verbatim terms are summarized separately according to the coded information of prior and concomitant medication.

#### **5.2.7. Protocol deviations**

All protocol deviations are recorded, classified, and summarized in a list. Prior to database locking, all protocol deviations are reviewed and discussed by relevant researchers and investigators of the sponsor project team.

Protocol deviations are classified as "critical", "major", and "general".

Critical and major protocol deviations are summarized according to the types of deviations and the enrolled population. Protocol deviations will also be listed in detail by subject.

### **5.3. Treatment Compliance**

The use of study drugs SHR-1210 and apatinib in the treatment period is summarized by descriptive statistics. Treatment compliance is summarized by using indexes such as relative dose intensity value.

### **5.4. Efficacy Analysis**

ORR and DCR are analyzed based on FAS and ES. Other efficacy analyses are performed based on FAS.

All efficacy analyses are performed according to the following populations (population with systemic first-line treatment, population without systemic first-line treatment, and total population).

### **5.4.1. Primary efficacy analysis**

The primary efficacy endpoint in this study is objective response rate (ORR) assessed by IRC based on RECIST v1.1. Full analysis set is the primary analysis set.

#### **5.4.1.1. Objective response rate (ORR)**

See Section 4.1.1 for the definition of objective response rate.

For the primary endpoint ORR, the proportion of all enrolled subjects whose best overall response (BOR) is assessed as complete response (CR) or partial response (PR) as per RECIST v1.1 is descriptively summarized. The ORR is calculated along with the corresponding two-sided 95% CI calculated using the Clopper-Pearson method. Data of best overall response evaluation will be listed and summarized.

### **5.4.2. Secondary efficacy analysis**

#### **5.4.2.1. Objective response rate (ORR)**

For secondary endpoints, ORRs assessed by investigators based on RECIST v1.1 and by IRC based on mRECIST are analyzed by using the aforementioned statistical methods for primary efficacy analysis.

#### **5.4.2.2. Progression-free survival (PFS)**

See Section 4.1.2.6 for the definition of progression-free survival (PFS).

Secondary endpoint PFS is calculated in months by using the following formula:  $(\text{PFS event date/censoring date} - \text{date of first administration} + 1) / 30.4375$ .

Kaplan-Meier method is used to analyze PFS, and the median time (month) of PFS is calculated. Brookmeyer-Crowley method is used to estimate the two-sided 95% CI of median time, and the PFS curve is drawn. The 6/9/12-month PFS rates are estimated by Kaplan-Meier method, and the corresponding 95% CIs are calculated using the log-log transformation according to normal distribution approximation with back transformation to CIs on the untransformed scale. The number and percentage of subjects with PFS of at least 6/9/12 months are calculated.

At the same time, the number and percentage of PFS events as well as the censoring number and percentage are calculated and classified according to the reason for censoring.

#### **5.4.2.3. Time to response (TTR)**

See Section 4.1.2.3 for the definition of time to response (TTR).

The calculation of secondary endpoint TTR only includes subjects showing a response. TTR is calculated in months by using the following formula:  $(\text{TTR event date} - \text{date of first administration} + 1) / 30.4375$ .

TTR (month) is described by mean, standard deviation, median, maximum, minimum, and quartile (Q1 and Q3) according to the population.

#### **5.4.2.4. Time to progression (TTP)**

See Section 4.1.2.4 for the definition of time to progression (TTP).

Secondary endpoint TTP is calculated in months by using the following formula: (TTP event date/censoring date - date of first administration + 1) / 30.4375.

Kaplan-Meier method is used to analyze TTP, and the median time (month) of TTP is calculated. Brookmeyer-Crowley method is used to estimate the two-sided 95% CI of median time, and the survival curve is drawn. The number and percentage of subjects with TTP of at least 6/9/12 months are calculated.

At the same time, the number and percentage of TTP events as well as the censoring number and percentage are calculated and classified according to the reason of censoring.

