#### **5.4.2.5. Duration of response (DOR)**

See Section 4.1.2.5 for the definition of duration of response (DOR).

Secondary endpoint DOR is calculated in months by using the following formula: (DOR event date/censoring date - date of first response + 1) / 30.4375.

DOR is analyzed only in subjects who have the best overall response of tumor response after treatment. The ending date of response must be consistent with the date of PD of PFS or death.

Kaplan-Meier method is used to calculate the median DOR in each treated population.

Brookmeyer-Crowley method is used to estimate the two-sided 95% CI of median time, and the survival curve is drawn. The 6/9/12-month DOR rates are estimated by Kaplan-Meier method, and the corresponding 95% CIs are calculated using the log-log transformation according to normal distribution approximation with back transformation to CIs on the untransformed scale.

The response date is the date of the first observed response.

In addition, descriptive statistics such as the number of subjects, minimum, maximum, and quartile (Q1 and Q3) are used to summarize the DOR data. If the maximum values are the censoring data, they will be displayed in the form of "xx+". The number and percentage of subjects with DOR of at least 6/9/12 months are calculated. At the same time, the number and percentage of DOR events as well as the censoring number and percentage are calculated and classified according to the reason of censoring.

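### For TTP, the SAP's only 6/9/12-month summary is a crude percentage that counts subjects censored before the landmark as failures; it should be a Kaplan-Meier rate, as for PFS, DOR and OS

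*SAP*

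**What the plan says.** **TTP (SAP 5.4.2.4).** The section states "Kaplan-Meier method is used to analyze TTP, and the median time (month) of TTP is calculated", with a Brookmeyer-Crowley interval for the median and a survival curve. Its only landmark summary is "The number and percentage of subjects with TTP of at least 6/9/12 months are calculated". The value entered for each subject is ("TTP event date/censoring date - date of first administration + 1) / 30.4375", so a censored subject's TTP is the time to censoring.

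**TTP censoring (SAP 4.1.2.4).** Death before progression, new anti-cancer treatment before progression, and progression after two or more missed visits are all censored at the last valid evaluation beforehand. A subject with no post-baseline evaluation is censored at first dose.

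**PFS and DOR (SAP 5.4.2.2 and 5.4.2.5).** Both have Kaplan-Meier landmark rates with log-log intervals: "The 6/9/12-month PFS rates are estimated by Kaplan-Meier method" and "The 6/9/12-month DOR rates are estimated by Kaplan-Meier method". Both also have crude counts: "The number and percentage of subjects with PFS of at least 6/9/12 months are calculated" and "The number and percentage of subjects with DOR of at least 6/9/12 months are calculated". OS rates (SAP 5.4.2.8) are by Kaplan-Meier only.

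**DOR quartiles (SAP 5.4.2.5).** In addition to the Kaplan-Meier median, "descriptive statistics such as the number of subjects, minimum, maximum, and quartile (Q1 and Q3) are used to summarize the DOR data". A censored maximum is marked with a plus sign.

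These analyses use the FAS (SAP 5.4). The denominator of the percentages is not written out. All FAS subjects, or all responders for DOR, is the natural reading, and nothing removes subjects censored early.

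**The concern.** The crude TTP percentage mixes two things: whether the subject progressed, and whether the subject was observed long enough to tell. A subject last scanned progression-free at 5 months is placed in the same group as one who progressed at 5 months. For PFS, DOR and OS the reader has a Kaplan-Meier rate to rely on. For TTP there is no tabulated alternative.

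Three consequences follow. The figure understates the proportion free of progression. It can change between the analysis at 6 months and the supplemental analysis at 12 to 24 months after the last first dose (protocol 4.5) with no change in drug effect. It can also differ between the two prior-treatment populations because their follow-up differs. The pretreated group may be enlarged to 120 late in the trial (protocol 11.1), so at an early cut-off its later entrants may have less follow-up.

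**Working it through.** The documents state no figure to reproduce. The numbers below are illustrations under stated assumptions.

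**1. What a censored subject contributes.** Scans are every 8 weeks for 12 cycles, then every 12 weeks (protocol 7.1.2). By the SAP formula they fall at (56 + 1)/30.4375 = 1.87 months, then 3.71, 5.55, 7.39, 9.23, 11.07 and 13.83. A progression-free subject with exactly 6 months of follow-up is censored at 5.55 and counted as below 6. A subject with no post-baseline scan has TTP = 1/30.4375 = 0.03 months and fails every landmark.

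**2. Formula.** With independent censoring, crude(m) = S(m) × G(m). S(m) is the probability of being progression-free to month m, and G(m) is the probability of still being under observation then. Kaplan-Meier estimates S(m).

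**3. Continuous time.** Assumptions: exponential TTP with median 5.5 months; uniform accrual over 9 months (March to December 2018, the anticipated dates); cut-off 6 months after the last first dose, so follow-up is uniform on 6 to 15 months; dropout of 2-4% per month.

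| Month | S = 2^(-m/5.5) | Administrative factor (15 - m)/9 | Dropout factor, 4% to 2% | Crude |
|---|---|---|---|---|
| 6 | 47% | 1 | 0.787-0.887 | 37-42% |
| 9 | 32% | 0.667 | 0.698-0.835 | 15-18% |
| 12 | 22% | 0.333 | 0.619-0.787 | 5-6% |

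At a cut-off 12 months after the last first dose the administrative factor is 1 throughout. The crude values become 37-42%, 22-27% and 14-17%, so what remains is due to the assumed dropout.

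**4. With the scan schedule.** Assumptions: median 6 months, same accrual, no dropout. A recorded TTP of at least 6 months needs no progression at the 5.55-month scan and follow-up to the 7.39-month scan. For 9 months the scans are 7.39 and 9.23; for 12 months they are 11.07 and 13.83.

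- Kaplan-Meier: 2^(-5.55/6) = 53%, 2^(-7.39/6) = 43%, 2^(-11.07/6) = 28%.
- Crude, 6-month cut-off: 0.527 × (15 - 7.39)/9 = 45%; 0.426 × (15 - 9.23)/9 = 27%; 0.278 × (15 - 13.83)/9 = 4%.
- Crude, 12-month cut-off: equal to Kaplan-Meier at 6 and 9 months; at 12 months 0.278 × (21 - 13.83)/9 = 22%.
- Crude, 24-month cut-off: equal to Kaplan-Meier at all three.

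A simulation (400 replicates, N = 120 + 56 = 176) gave 45/28/4% crude against 53/43/28% at the 6-month cut-off. Over medians of 4 to 9 months, the 12-month figure there was 2-6% crude against 14-43%.

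**5. Early censoring at the 24-month cut-off** (simulated, median 6):

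| Scenario | Crude 6/9/12 | Kaplan-Meier 6/9/12 |
|---|---|---|
| 20% censored early by month 12 | 46/36/22% | 53/43/28% |
| 10% censored early, plus death without progression (assumed median 24 months) | 40/30/17% | 53/43/28% |

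**6. DOR quartiles, if computed as plain quantiles** (simulated, 50 responders):

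| Assumed median DOR | Cut-off | Plain Q1 (true) | Plain Q3 (true) | Kaplan-Meier Q3 not reached |
|---|---|---|---|---|
| 9 months | 6 months | 3.2 (3.7) | 8.0 (18) | 85% |
| 9 months | 12 months | 4.0 (3.7) | 12.3 (18) | 54% |
| 9 months | 24 months | 3.9 (3.7) | 17.6 (18) | 1% |
| 15 months | 6 months | 4.1 (6.2) | 8.8 (30) | 96% |
| 15 months | 12 months | 6.5 (6.2) | 13.9 (30) | 92% |
| 15 months | 24 months | 6.5 (6.2) | 23.3 (30) | 51% |

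Q3 carries the bias. Q1 is little affected, except when responses are long and follow-up is shortest.

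**The case against.** **TTP is not left without a censoring-aware analysis.** A reader might infer that it is. The documents do not support that: the Kaplan-Meier median, its interval and the curve are planned, and a landmark value can be read off the curve. What is missing is a tabulated rate with its interval, while the tabulated figure is the biased one.

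**PFS and DOR are already covered.** A reader might infer that their landmark results are biased too. They are not: the Kaplan-Meier rates are specified in the same sections, and the crude counts are supplementary. Nor must the two figures disagree, since in step 4 they coincide at 6 and 9 months with a 12-month cut-off. This part of the objection stands, and labelling is enough.

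**Plain DOR quartiles are an inference.** For uncensored TTR the SAP lists mean, standard deviation and median. For DOR it omits these from the descriptive list, takes the median from Kaplan-Meier and flags a censored maximum. Kaplan-Meier quartiles cannot be excluded. Even so, quartiles are listed as descriptive statistics in addition to the Kaplan-Meier median, and SAP 5.1.2 names Kaplan-Meier for the survival function and median only. Plain quantiles are the likelier reading, and the text should settle it.

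**The early cut-off may not be the one that matters.** The SAP plans 15- and 18-month OS rates, and 18 months cannot be reached with at most 15 months of follow-up. SAP versions 1.0 and 2.0 are dated March 2020 and April 2021, against anticipated last enrolment in December 2018. This suggests, without proving, longer follow-up. It stands as a limit on the size of the bias, but step 5 shows that the early-censoring part persists.

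**Kaplan-Meier with deaths censored is itself hypothetical.** It assumes that subjects who died would otherwise have progressed as the survivors did. This stands and should be stated beside the rate. It does not rescue the crude percentage, which counts those deaths as failures at every later landmark although the endpoint censors them.

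**Conclusion.** The point holds for TTP. The only tabulated 6/9/12-month TTP figure is biased downwards whenever subjects are censored before the landmark.

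The size is conditional. Under assumed exponential times with a median of 5.5 to 6 months and 9 months of uniform accrual, the 12-month figure is about 4-6% crude against 22-28% at the 6-month cut-off. By 24 months the administrative part is gone, and the gap comes only from dropout, new therapy, missed visits and death: none without early censoring, and 6 to 13 percentage points in the two scenarios of step 5. The documents fix neither the TTP distribution nor the amount of early censoring, so no single figure can be given.

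For DOR quartiles this is an ambiguity to resolve, with Q3 at risk. For PFS and DOR landmarks it is a matter of labelling. A reader might infer that the trial's efficacy conclusion is at stake. It is not: TTP is absent from the protocol's endpoints and was added as a secondary endpoint in the SAP, and the decision rules (SAP 3) rest on ORR alone. Minor to moderate.

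**What to change.** - **SAP 5.4.2.4:** replace the crude percentages by Kaplan-Meier 6/9/12-month TTP rates with log-log 95% intervals, as in 5.4.2.2. Add that deaths before progression are censored, so the rate describes progression with death treated as independent censoring.
- **SAP 5.4.2.5:** state that DOR Q1 and Q3 are taken from the Kaplan-Meier curve, and are shown as not reached where the curve does not fall far enough.
- **SAP 5.4.2.2 and 5.4.2.5:** label the crude PFS and DOR figures as the number of subjects observed event-free to the landmark, and point to the Kaplan-Meier rate as the estimate. They need not be deleted.

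The cost is SAP wording and table shells. The analysis that gives the planned curves and the PFS rates also gives these estimates. No data collection, sample size or primary analysis changes.

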#### **5.4.2.5. Duration of response (DOR)**

See Section 4.1.2.5 for the definition of duration of response (DOR).

Secondary endpoint DOR is calculated in months by using the following formula: (DOR event date/censoring date - date of first response + 1) / 30.4375.

DOR is analyzed only in subjects who have the best overall response of tumor response after treatment. The ending date of response must be consistent with the date of PD of PFS or death.

Kaplan-Meier method is used to calculate the median DOR in each treated population.

Brookmeyer-Crowley method is used to estimate the two-sided 95% CI of median time, and the survival curve is drawn. The 6/9/12-month DOR rates are estimated by Kaplan-Meier method, and the corresponding 95% CIs are calculated using the log-log transformation according to normal distribution approximation with back transformation to CIs on the untransformed scale.

The response date is the date of the first observed response.

In addition, descriptive statistics such as the number of subjects, minimum, maximum, and quartile (Q1 and Q3) are used to summarize the DOR data. If the maximum values are the censoring data, they will be displayed in the form of "xx+". The number and percentage of subjects with DOR of at least 6/9/12 months are calculated. At the same time, the number and percentage of DOR events as well as the censoring number and percentage are calculated and classified according to the reason of censoring.

#### **5.4.2.6. Disease control rate (DCR)**

See Section 4.1.2.2 for the definition of disease control rate (DCR).

The analysis method of secondary endpoint DCR is the same as that of ORR.

#### **5.4.2.7. Overall survival (OS)**

See Section 4.1.2.7 for the definition of overall survival (OS).

OS is calculated in months by using the following formula:  $(\text{OS event date/censoring date} - \text{date of first administration} + 1) / 30.4375$ .

Kaplan-Meier method is used to analyze OS, and the median survival time of each treated population is calculated. Brookmeyer-Crowley method is used to estimate the two-sided 95% CI of median time, and the overall survival curve is drawn. Follow-up time (month) is described by the number of subjects, median, maximum, minimum, and quartile (Q1 and Q3) according to the population. If the maximum values are the censoring data, they will be displayed in the form of "xx+".

At the same time, the number and percentage of OS events as well as the censoring number and percentage are calculated and classified according to the reason of censoring.

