4.5. Definition of Study Completion

The study is completed at 6 months after the first dose of the last subject, and the primary and secondary endpoints of the study are statistically analyzed.

All subjects will be followed up until 12 to 24 months after the dosing of the last subject, and supplemental analysis of the primary and secondary endpoints of the study will be performed after the follow-up.

After the end of the study, if the subjects may continue to benefit from the investigational drug, the treatment can be continued until the criteria for discontinuation are met. The occurrence of SAEs will be collected and recorded during the treatment and after the last dose according to the protocol.

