17. CLINICAL TRIAL PROGRESS

Anticipated enrollment of the first subject: March 2018

Anticipated enrollment of the last subject: December 2018

Anticipated study completion date: June 2019

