#### **4.1.2.7. Overall survival (OS)**

Overall survival (OS): It is defined as the time from the date of first administration to death due to any cause.

Censoring rules are as follows:

- If the subject withdraws and is still alive, the censoring date is the last follow-up date when the survival status is obtained.
- If the subject is lost to follow up, the censoring date is the last follow-up date when the survival status is obtained prior to the lost of follow-up.

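### SAP 5.4.2.7 leaves follow-up time undefined; on its natural reading the reported median counts deaths as the end of follow-up and understates how long the trial observed its subjects.

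*SAP*

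**What the plan says.** The only instruction on follow-up time is one sentence in SAP 5.4.2.7, the section on analysis of OS: "Follow-up time (month) is described by the number of subjects, median, maximum, minimum, and quartile (Q1 and Q3) according to the population". The next sentence gives a display rule: "If the maximum values are the censoring data, they will be displayed in the form of" a number with a plus sign.

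The only time variable defined in that section is OS in months: event or censoring date, minus date of first administration, plus 1, divided by 30.4375. SAP 4.1.2.7 defines OS itself: "It is defined as the time from the date of first administration to death due to any cause". For living subjects who leave the study it adds: "If the subject withdraws and is still alive, the censoring date is the last follow-up date when the survival status is obtained". The SAP nowhere mentions reverse Kaplan-Meier, and it does not define follow-up time in any other section.

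Protocol 4.5 sets a main analysis 6 months after the last subject's first dose, and then: "All subjects will be followed up until 12 to 24 months after the dosing of the last subject", with a supplemental analysis after that. Neither document gives an expected follow-up time or an expected median OS for the combination.

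**The concern.** A plus sign on a censored maximum makes sense only if some values in the series are not censored, that is, if they are deaths. SAP 5.4.2.5 uses the same marker for DOR, where event and censored times are summarised together by descriptive statistics. A programmer who follows 5.4.2.7 would therefore most likely take the ordinary median of observed OS times.

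In that series a death cuts follow-up short, although the subject's outcome is then fully known. The median becomes a mixture of how soon subjects die and how long the trial watched them. Once every subject has been observable for longer than median OS, the figure equals median OS, and further follow-up cannot raise it.

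Readers use median follow-up to judge whether DOR and the survival rates out to 18 months (SAP 5.4.2.8) are mature. The SAP also reports it by population, so the cohort with worse survival would look less well followed even if both cohorts had enrolled over the same period.

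**Working it through.** The documents state no follow-up figure, so there is none to reproduce. The check compares the plain median with the reverse Kaplan-Meier median under the planned timetable.

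**Inputs**
- Accrual (Protocol 17): "Anticipated enrollment of the first subject: March 2018" and "Anticipated enrollment of the last subject: December 2018". Taken as uniform over A = 9 months.
- Cut-off L months after the last first dose (Protocol 4.5): L = 6 for the main analysis, and 12 to 24 for the supplemental one.
- Median OS m, low: about 10 months (first-line sorafenib, Protocol 1.2.2; apatinib monotherapy 9.71 and 9.82 months, Protocol 1.1).
- Median OS m, middle and high: 12-month survival on nivolumab of 58-60% after sorafenib and 73% without prior sorafenib (Protocol 1.1). With exponential survival, m = 12 × ln 2 / (−ln S12), which gives 15.3, 16.3 and 26.4 months.
- Assumed: exponential OS, no loss to follow-up, and survivors observed up to the cut-off itself.

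**Formulas**
- Share of subjects with potential follow-up beyond t: G(t) = 1 for t ≤ L, and (L + A − t)/A for L < t < L + A.
- The plain median of observed OS time solves 0.5^(t/m) × G(t) = 0.5.
- The reverse Kaplan-Meier median estimates median potential follow-up, L + A/2.

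**Example, L = 6 and m = 10.** At t = 7.46, 0.5^0.746 = 0.596 and G = (15 − 7.46)/9 = 0.838; the product is 0.50. The plain median is 7.5 months, against 6 + 4.5 = 10.5. The shortfall is 1 − 7.46/10.5 = 29%.

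**Results** (months; shortfalls from unrounded medians)

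| Cut-off L | Reverse KM | Plain, m = 10 | Plain, m = 15.3-16.3 | Plain, m = 26.4 |
|---|---|---|---|---|
| 6 | 10.5 | 7.5 (29% low) | 8.4-8.5 (19-20% low) | 9.3 (12% low) |
| 12 | 16.5 | 10.0 (39% low) | 12.9-13.1 (20-22% low) | 14.4 (13% low) |
| 24 | 28.5 | 10.0 (65% low) | 15.3-16.3 (43-46% low) | 24.5 (14% low) |

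Simulation with 176 subjects (120 + 56) and 500 runs agrees with the plain medians to within 0.3 month and returns the same reverse Kaplan-Meier medians.

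**Sensitivity.** With m = 9.8 in place of 10, the largest shortfalls are 29%, 41% and 66%. With A = 10 months, the reverse Kaplan-Meier medians are 11, 17 and 29, and the shortfalls 13-31%, 14-41% and 16-66% for m from 10 to 26.4.

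**By population at L = 24.** Suppose both cohorts had the same accrual and the nivolumab survival rates. True median follow-up is 28.5 months in each. The plain median would be 15.3-16.3 months in the pretreated cohort and 24.5 in the other, an apparent gap of 8 to 9 months due to mortality alone. For the total population (59% and 73% alive at 12 months, pretreated share 80/136 or 120/176) it would be 19.3 or 18.4 months, which is 32-35% low.

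**When the shortfall exceeds half.** This needs m < (L + 4.5)/2, which is 5.25 months at L = 6, 8.25 at L = 12 and 14.25 at L = 24.

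**The case against.** The strongest reply is that the SAP does not say that deaths are included. The plus-sign rule could be template wording carried over from DOR. SAP 5.1.2 summarises ordinary continuous variables with mean and standard deviation, and 5.4.2.7 omits both for follow-up time, which might suggest a censored quantity handled by Kaplan-Meier. This stands in part: inclusion of deaths is an inference, not a stated rule. But an ordinary Kaplan-Meier median of the OS variable would only repeat median OS, and a reverse analysis would have to be specified in order to be run. The sentence needs correcting on either reading.

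A reader might infer that follow-up would be understated by more than half at the later cut-off. The documents do not support that in general. The later cut-off is a range; at 12 months no cited survival figure gives a shortfall of half, and at 24 months it takes a median OS below about 14 months. The roughly 10-month sorafenib and apatinib figures meet that condition, and the anti-PD-1 rates do not. A reader might also infer that the figure is pinned to median survival, or that extra follow-up hardly moves it. Neither holds throughout: at 6 months the plain median is 7.5 against a median OS of 10, and with m = 26.4 it rises from 9.3 to 14.4 to 24.5.

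The low impact is also a fair point. No decision rule or formal comparison uses follow-up time. The error makes the data look less mature, not more. Event and censoring counts, survival curves and swimmer plots show maturity by other routes. All of this stands and limits the weight of the point, but it does not make the figure correct.

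**Conclusion.** The point holds as a defect in a descriptive summary. SAP 5.4.2.7 does not define follow-up time, and its natural reading gives a median that is too low in every survival scenario the protocol's own figures support. Under the stated assumptions, the shortfall runs from 12% to 29% at the main cut-off and from 13% to 65% over the 12- to 24-month range. Its size depends mainly on median OS, which the documents do not predict for this combination.

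The practical harm is to interpretation. At the 24-month cut-off every subject would have at least 24 months of potential follow-up, yet a reported median of 10 to 16 months, as in the low and middle scenarios, would make the 15- and 18-month survival rates look immature. The cohorts would also seem unequally followed for reasons unrelated to follow-up. The ORR confidence limits and decision rules (SAP 3) and the Kaplan-Meier OS medians and rates (SAP 5.4.2.7 and 5.4.2.8) do not change.

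**What to change.** In SAP 5.4.2.7, replace the follow-up sentence and its display rule. State that follow-up time runs from first administration and is estimated by reverse Kaplan-Meier, with deaths treated as censored and censored subjects as events. Report the median, quartiles and 95% CI for each population and for the total. Add the minimum and maximum time from first dose to data cut-off. If the plain summary of observed OS time is kept, label it as that and do not report it as median follow-up.

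The cost is a small wording change and one further Kaplan-Meier run with the censoring indicator reversed. No new data are needed, and no other planned analysis changes.
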